11.4 Expected adverse events that do not require reporting to REC

Effects relating to the Cytosponge™ could include:

- Cytosponge™ detached from the string while in the patient's oesophagus/stomach (SADE)
- Inability or difficulty to remove the Cytosponge™ (SADE)
- Laceration at the back of the throat (ADE or SADE depending on Bleeding and size of the laceration)
- Perforation or tear of the oesophagus (SADE)
- Bleeding from biopsy site or Cytosponge™ abrasion (SADE)
- Obstruction on breathing or airway as a result of the Cytosponge™ (SADE)
- Mild sore throat (ADE)

11.5 Reporting of SAEs to the Trial Office

All SAEs & SADEs must be reported on the study-specific SAE Form and sent to:

Pharmacovigilance Office, OCTO

Email: [contact]

[contact]

SAE forms must be completed and submitted within **24hrs** of becoming aware of the event. If the SAE has not been reported within the specified timeframe, a reason for lateness must be provided when sending the SAE Report Form. For the initial report the following elements must be completed:

- Overall diagnosis (CTCAE grading)
- Reason for seriousness
- Causality (must be assessed by a medically qualified person)
- Name and signature of the reporting person

Any change of condition or other follow-up information should be sent by sites to the Pharmacovigilance office, as soon as it is available or at least within 24 hours of the information becoming available. Events will be followed up until the event has resolved or a final outcome has been reached.

Each separate AE episode must be recorded. For example, if an AE resolves completely or resolves to baseline and then recurs or worsens again, this must be recorded as a separate AE. For AEs to be considered intermittent, the events must be of similar nature and severity.

11.6 Follow-up of Serious Adverse Events

A follow-up report must be completed when the SAE resolves, is unlikely to change, or when additional information becomes available. If the SADE is a suspected USADE then follow up information must be provided as requested by the Trial Office.

If new or amended information on a reported SAE becomes available, the Investigator should report this on a new SAE form using the completion guidelines. If this is not possible and any changes are made to the original completed form, you must initial and date all new or amended information so that all changes are clearly identified.

SAEs that are considered to be definitely unrelated to the trial intervention will not be followed up and monitored.

11.7 Reporting AEs to the MHRA and REC

Reporting to the MHRA: All SAEs, will be reported **immediately** to the MHRA (devices) by the Sponsor or delegate (see further timings under Urgent Safety Reporting). This is irrelevant of whether the event is believed to be device related or not.

Urgent safety reporting:

Any SAE, SADE or USADE which indicate an imminent risk and require prompt remedial action, or new finding related to such an event, will be reported to the MHRA immediately, but no later than 2 calendar days following awareness by the sponsor or delegate.

Any other SAEs, SADEs or USADEs, or new finding/update, will be reported immediately to the MHRA, but no later than 7 calendar days after awareness by the sponsor or delegate.

Any urgent safety measures will be reported to the MHRA and REC within 3 days of the measures being implemented.

Reporting to the REC: All SADEs & USADEs, other than those listed in section 11.4, will be reported to the REC by the Chief Investigator in conjunction with the Sponsor within 15 days of the CYTOFLOC Trial Office & CI becoming aware. This will follow the current HRA guidance: <http://www.hra.nhs.uk/resources/during-and-after-your-study/progress-and-safety-reporting/> Safety aspects will be addressed in the Annual Progress Report to the REC by the Chief Investigator. Please see further guidance under Urgent Safety Reporting.

Anonymised data may be shared with the manufacturer and their associates for safety and product development purposes.

11.8 Reporting Adverse Events on the CRF

All AEs, including Serious AEs must be recorded on the case report forms (CRF) for that patient (unless otherwise specified in section 11.9. The information provided will include date of onset, event diagnosis (if known) or sign/symptom, severity, time course, duration and outcome and relationship of the AE to device. Any concomitant medications or any other therapy used to treat the event must be listed. The Investigator will provide an "other" cause for serious AEs considered to be unrelated to the study device. Sites should ensure data entered into the CRF is consistent with the SAE report information where applicable.

Each separate AE episode must be recorded. For example, if an AE resolves completely or resolves to baseline and then recurs or worsens again, this must be recorded as a separate AE. For AEs to be considered intermittent, the events must be of similar nature and severity.

AEs may be spontaneously reported by the patient and/or in response to an open question from study personnel or revealed by observation, physical examination, or other diagnostic procedures. Any clinically relevant deterioration in laboratory assessments or other clinical finding is considered an AE.

AEs which are serious must be reported to OCTO from the time of Cytosponge™ administration until the participant completes the study at the Two Week Telephone Follow Up appointment. If a participant receives surgery prior to this point, the safety reporting period will be up until the participant receives surgery (see section 5.3, Telephone Follow-Up Evaluations (End of Study)). Should an Investigator become aware of any study intervention related Serious Adverse Device Effects (SADEs) following the Two Week Telephone Follow Up, these must also be reported to OCTO.

Terms and Grading of Events

The NCI CTCAE Version 4.0 (currently up to Version 4.03) must be used by the site for grades; the events will be coded in-house by the Pharmacovigilance team using MedDRA and where possible using the Lowest Level Terms provided. Where indicated on the SAE form, provide the severity grade, and the worst grade recorded.

11.9 Events exempt from being reported as AE/SAE

Progression of underlying disease

Disease progression and resultant death will be captured on the CRF. Adverse events including hospitalisation that are clearly consistent with disease progression will not be reported as individual AE/SAEs. Clinical symptoms of progression will only be reported as adverse events if the symptom cannot be determined as exclusively due to the progression of the underlying malignancy, or does not fit the expected pattern of progression for the disease under study.

Every effort should be made to document the objective progression of underlying malignancy. In some cases, the determination of clinical progression may be based on symptomatic deterioration. For example, progression may be evident from clinical symptoms, but is not supported by tumour measurements. Or, the disease progression is so evident that the investigator may elect not to perform further disease assessments.

Elective admissions and supportive care

Planned hospitalisation for a pre-existing condition, or a procedure required by the CIP [Clinical Investigation Plan], without serious deterioration in health, is not considered a serious adverse event, and do not require SAE reporting.

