For the Cytosponge™ to have a wider application in oesophageal cancer, including treatment surveillance, a feasibility study is required. One of the important differences from patients with BE is that these patients already have dysphagia which could make swallowing of the capsule or retrieval of Cytosponge™ more difficult. Secondly, radiotherapy would have resulted in inflammation of the surrounding tissue. Sample analysis should be robust enough to differentiate molecular markers of inflammation from that of residual cancer. Finally, although a molecular marker for BE and dysplasia that can be detected by Cytosponge™ is well defined and assessed through immunohistochemistry Trefoil Factor 3 (TFF3) and p53 sequencing, markers for invasive cancer detectable with this device need to be developed and validated.

Benefits

This study will test the acceptability and feasibility of using Cytosponge™ post chemo-radiation. The participants will not benefit directly. However, if this study shows feasibility/acceptability, it will lead to larger studies evaluating its role in surveillance post-dCRT, using the Cytosponge™ at multiple time-points during follow-up. An effective surveillance programme may detect a greater proportion of patients with local-only recurrences treatable by curative salvage resection. It may also lead to a shift in standard care where patients could be offered dCRT as first choice, keeping surgery in reserve for patients who fail dCRT.

Risks

The risk for Cytosponge™ in patients with oesophageal cancer has not been assessed previously. It has however, been tested in >1000 patients with Barrett's esophagus. The most common side-effect is a sore throat. Rare complications could be bleeding, perforation, effects on the airway, the Cytosponge™ getting stuck beyond the tumour or detachment of the Cytosponge™ from the string requiring endoscopy to recover the Cytosponge™.

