14 STATISTICAL ANALYSIS PLAN

The completion rate (swallowing of the sponge, retrieval of the sponge without additional intervention) with corresponding 95% confidence interval will be calculated at the end of the trial. Results will be given for all patients and also separately for (1) patients recruited post dCRT and (2) patients recruited post naCRT.

Stopping rules: The study will be stopped if there is more than one serious life-threatening complication from the Cytosponge™ (e.g. oesophageal perforation or life-threatening gastro-intestinal bleeding).

A statistical analysis plan will be finalised before release of the final data set.

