#### 6.1.2 Secondary feasibility outcomes

**Safety:** defined as all serious adverse events (including bleeding requiring transfusion and perforation) that occur between from the time of Cytosponge™ administration (D1) and when the patient completes the study at the two week telephone follow-up. If a participant undergoes surgery prior to their two week follow up visit, then their safety reporting period continues until the time of surgery. Adverse events will also be reported. Severity rating of adverse effects will be as per the Common Terminology Criteria for Adverse Events (CTCAE) V4.03.

**Consent rate:** defined as the proportion of eligible patients who consent to take part in the study.

**Acceptance rate:** defined as the proportion of patients who have successfully undergone the Cytosponge™ procedure and would be prepared to accept the procedure repeatedly if it was to be used for follow-up.

**Suitability of sample for biomarker analysis:** defined as the percentage of samples from the Cytosponge™ test with the presence of cytological atypia and/or p53 abnormality (also called “positive samples”).

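### The progression exemption in Protocol 11.9 uses two unequal tests and has no exception for listed device effects, so a misattributed device harm could go uncounted with no causality record

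*Protocol*

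**What the plan says.** Protocol 11.9 sets the exemption: "Adverse events including hospitalisation that are clearly consistent with disease progression will not be reported as individual AE/SAEs". The next sentence covers symptoms: "Clinical symptoms of progression will only be reported as adverse events if the symptom cannot be determined as exclusively due to the progression" of the malignancy. A symptom that does not fit the disease's expected pattern also stays reportable. The section asks for objective documentation of progression but accepts that "progression may be evident from clinical symptoms, but is not supported by tumour measurements". Progression itself, and death from it, still go on the CRF.

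Other sections bear on this:

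- Protocol 11.8 requires every AE on the CRF, with its relationship to the device, except where 11.9 provides otherwise.
- Protocol 11.2 requires a causality assessment of each AE and names progressive malignancy among the possible causes.
- Protocol 11.4 lists perforation or tear, bleeding and airway obstruction among the possible device effects. Protocol 1.3 (Risks) says: "Rare complications could be bleeding, perforation, effects on the airway, the Cytosponge™ getting stuck beyond the tumour", among others.
- Protocol 11.7 sends all SAEs to the MHRA and adds: "This is irrelevant of whether the event is believed to be device related or not".
- SAP 6.1.2 describes the safety outcome as "defined as all serious adverse events (including bleeding requiring transfusion and perforation) that occur between" device administration and the two-week call, or surgery if that comes first.
- Protocol 14 gives the stopping rule: "The study will be stopped if there is more than one serious life-threatening complication from the Cytosponge™".

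**The concern.** The two sentences in 11.9 set different thresholds, and the text does not say which governs. The looser one covers hospitalisation, which is itself a seriousness criterion in 11.1. Someone admitted with bleeding some days after the procedure may be judged clearly consistent with progression by one investigator, while another would not call progression the exclusive cause.

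The exemption also acts before the step designed to separate device from disease. Section 11.2 already lets the investigator attribute an event to malignancy and leaves a record of that judgement. Section 11.9 lets the site reach the same conclusion without the record.

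At stake is the safety outcome. Protocol 1.3 says there are no safety data for this device in carcinoma patients after dCRT. The counts will be very small, and there is no independent DSMC (Protocol 16.2). SAP 3.4 has the TMG pass complications to the oversight committee, so that committee depends largely on what sites report. An error of this kind can only lower the count of device harms.

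**Working it through.** **1. The plan's own figure.** Protocol 13.1 and SAP 3.3 give ±13% for 50 patients at a 70% completion rate. The asymptotic half-width is 1.96 × √(0.7 × 0.3 / 50) = 1.96 × 0.0648 = 0.127, so the figure reproduces. The exemption does not touch it, because completion means swallowing and retrieval without additional intervention. Only the safety counts are affected.

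**2. Path of one event.** Take a bleed leading to admission after the procedure.

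- *Site does not invoke 11.9:* CRF entry with relationship to device (11.8), causality assessment (11.2), SAE form within 24 hours (11.5), report to the MHRA (11.7), inclusion in the SAP 6.2.2 tables.
- *Site invokes 11.9:* no individual AE or SAE report and no required CRF entry for the event. Nothing then feeds 11.7 or SAP 6.2.2. Neither 11.7 nor the SAP refers to 11.9, and the SAP has no listing of exempted events.

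The branch turns on a judgement for which 11.9 gives two thresholds.

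**3. Weight of one event.** The safety population is all who attempt to swallow the device (SAP 4.2), taken here as 50. One event is 1/50 = 2 percentage points. Exact (Clopper-Pearson) 95% upper limits are 7.1% for 0/50, 10.6% for 1/50 and 13.7% for 2/50.

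**4. Monitoring thresholds.** The stopping rule is met at the second life-threatening complication. The TMG meeting trigger (Protocol 3, footnote) is more than three transfused procedure-related bleeds, so it is met at the fourth. Let q be the true rate of the relevant device harm and f the share of those harms exempted as progression. The documents give neither; both are assumptions for illustration. With π = q(1 − f), the count is binomial(50, π), and

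P(2 or more) = 1 − (1 − π)^50 − 50π(1 − π)^49.

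For q = 5% and f = 0: 1 − 0.0769 − 0.2025 = 0.721. The remaining results are:

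| q (assumed) | Threshold | f = 0 | f = 25% | f = 50% |
|---|---|---|---|---|
| 2% | 2 or more | 26.4% | 17.3% | 8.9% |
| 5% | 2 or more | 72.1% | 56.4% | 35.6% |
| 10% | 2 or more | 96.6% | 89.7% | 72.1% |
| 5% | 4 or more | 24.0% | 11.7% | 3.6% |
| 10% | 4 or more | 75.0% | 52.2% | 24.0% |

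In these rows q refers to life-threatening complications for the threshold of two and to transfused bleeds for the threshold of four. The table shows how sensitive the thresholds are to lost events. It does not estimate how many will be lost.

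**The case against.** The best defence is that the second sentence of 11.9 limits the first. A symptom with a plausible device contribution cannot be called exclusively due to progression, and a symptom outside the expected pattern stays reportable too. Deciding on exclusivity is itself a causal judgement. The exemption names AEs and SAEs, whereas 11.5 requires SADEs to be reported within 24 hours and 11.4 classes perforation, device bleeding and airway obstruction as SADEs. The window is about two weeks and ends at surgery.

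Much of this stands. Read carefully, 11.9 should not lose a device event, so loss needs a misjudgement or reliance on the looser sentence. But the SADE and causality provisions apply only once the site has decided that the event is not progression. They do not protect against error in that decision.

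A reader might infer more than the documents support:

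- *That an early bleed in a patient with residual tumour is exempt as written.* It is not: the looser test still requires the event to be clearly consistent with progression, and residual tumour is not progression.
- *That the exempt events are the endpoint events.* The endpoint in Protocol 3 and SAP 2.2 is procedure-related serious effects, which overlap with the exempt set only through misattribution. The documents do not describe bleeding, perforation or airway events as expected features of progression, so the clinical overlap is an inference.
- *That nobody would review the decision.* Progression is captured on the CRF, data are checked against source (Protocol 22.2), and the TMG and oversight committee have safety roles. What is missing is a defined review of exempted events. The monitoring plan and the committee's charter are not available here.
- *That counting these harms is the trial's main purpose.* Completion rate is primary; safety is secondary.

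**Conclusion.** The point holds as a gap in the reporting rule, not as evidence that events will be lost. Section 11.9 has two unequal tests and no exception for the effects in 11.4, and 11.8 removes the record that would let anyone check the decision. This does not fit with 11.7 or with SAP 6.1.2. Under the all-SAE definition in SAP 6.1.2, even a correct exemption takes an event out of the count.

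Any loss of a true device harm runs in one direction, towards a safer-looking device. Its size cannot be stated, because the documents give no progression rate and no device-harm rate for the window. What is certain is that each event is 2 points of 50 and that the second life-threatening complication meets the stopping rule, so one misattributed event could decide whether the rule is met. If 2% to 10% of patients (an assumption) had a bleed, perforation or airway event in the window, that would be 1 to 5 of 50. It would be wrong to treat all of those as exempt, since most should fail the stricter test. The change is worth making because it is cheap and the counts are small.

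**What to change.** In Protocol 11.9, drop the looser test and keep one rule: an event is exempt only if it is exclusively due to progression. Add that events of a type listed in 11.4 (bleeding, perforation or tear, airway obstruction) within the safety reporting period are always recorded as AE or SAE and given a causality assessment under 11.2, even when progression is the likely cause. A carve-out for dysphagia would add little, as dysphagia is already scored on day 1 and at the week 1 and week 2 calls where these precede surgery.

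In SAP 6.2.2, add a listing of any in-window event exempted under 11.9, with timing relative to the procedure and a causality assessment. SAP 3.1 gives the end of recruitment as 31 January 2020 and SAP version 1.0 is dated 22 April 2020, so for this trial the SAP listing is the practical route. Because 11.8 excuses exempt events from the CRF, sites would have to be queried for them.

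The cost is a sentence and a deletion in the protocol, one listing in the SAP, a site query, and a few extra forms in about 50 patients, some of which will be judged unrelated.

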12 DEFINING THE END OF STUDY

For this study the end of the study is defined as “The last visit of the last patient undergoing the study (LPLV)”. Telephone follow ups are included as visits.

Recruitment to the study will be stopped when:

- The stated number of patients to be recruited is reached.
- The stated primary and secondary objectives of the study are achieved.

The Sponsor and the Chief Investigator reserve the right to terminate the study earlier at any time. In terminating the study, they must ensure that adequate consideration is given to the protection of the participants’ best interests.

13 STATISTICAL CONSIDERATIONS

13.1 Sample size and power

The trial aims is to recruit 50 evaluable patients in 24 months from approximately 10 UK centres to give a completion rate estimate to +/-13% for feasibility (95% CI, estimated 70% rate) and enough samples to consider markers. Participants that do not receive the intervention will be withdrawn and replaced at the Chief Investigator’s discretion.

14 STATISTICAL ANALYSIS PLAN

The completion rate (swallowing of the sponge, retrieval of the sponge without additional intervention) with corresponding 95% confidence interval will be calculated at the end of the trial. Results will be given for all patients and also separately for (1) patients recruited post dCRT and (2) patients recruited post naCRT.

Stopping rules: The study will be stopped if there is more than one serious life-threatening complication from the Cytosponge™ (e.g. oesophageal perforation or life-threatening gastro-intestinal bleeding).

A statistical analysis plan will be finalised before release of the final data set.

14.1 Inclusion in analysis

To be evaluable for assessment of the study primary endpoint, participants must have attempted to swallow the Cytosponge™.

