14.5 Final analysis

Final analysis will be after end of study evaluations have been recorded and data has been checked to be complete and accurate. Decision to proceed to a formal phase II will be determined by whether the primary and secondary objectives of this study have been met. If the completion rate is >70% then the trial outcome will be to develop a randomised phase II/ III testing Cytosponge™ in post-CRT follow-up.

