### 3.3 Sample Size

The trial aims to recruit 50 evaluable patients in 24 months from approximately 10 UK centres to give a completion rate estimate to +/-13% for feasibility (asymptotic 95% CI, estimated 70% rate) and enough samples to consider markers. Participants that do not receive the intervention will be withdrawn and replaced at the Chief Investigator's discretion.

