## 5.5 Description of Compliance with Intervention

The number of eligible, consented patients who complete the Cytosponge™ procedure overall and in each subgroup (having received dCRT and naCRT) will be reported. The number of eligible patients who return the questionnaire and have a telephone interview at one and two weeks (i.e. those who do not have surgery in the two weeks after the Cytosponge™ procedure) will also be reported. Deviations from intended treatment (non-adherence to protocol) including losses to follow-up and withdrawals will be summarised.

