## 6. ANALYSIS

### 6.1 Definitions of feasibility outcomes

#### 6.1.1 Primary feasibility outcome

The primary outcome measure is the completion rate, defined as the proportion of consented, evaluable participants who are able to successfully undergo the Cytosponge™ procedure. i.e. patients who are able to swallow the sponge and have the sponge retrieved without additional intervention. Evaluable participants are those who have attempted to swallow the Cytosponge™.

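### The completion rate and its >70% go rule cover only patients who attempt the swallow, so a consented non-attempter who has not withdrawn consent is a failure in no planned rate

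*Protocol*

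**What the plan says.** **Denominator.** Protocol 14.1: "To be evaluable for assessment of the study primary endpoint, participants must have attempted to swallow the Cytosponge™". SAP 6.1.1: "Evaluable participants are those who have attempted to swallow the Cytosponge™". Protocol 6.1 and SAP 3.7, 4.2 and 6.2.1 agree.

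**Success.** The sponge must be swallowed and brought back with no extra intervention (Protocol 14, SAP 6.1.1). An attempter who cannot swallow it, or who needs help with retrieval, stays in the denominator as a failure.

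**Replacement.** Protocol 6.1 and SAP 6.2.1 let the Chief Investigator replace patients who are not evaluable. Protocol 13.1 and SAP 3.3 use a different trigger, not having received the intervention. The target is to "recruit 50 evaluable patients in 24 months from approximately 10 UK centres".

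**Go rule.** Protocol 14.5, repeated in SAP 3.7: "If the completion rate is >70% then the trial outcome will be to develop a randomised phase II/ III". The sentence before it makes the decision to proceed depend on the secondary objectives as well, without numerical thresholds for them.

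**Where non-attempters appear.** SAP 5.2 reports withdrawals with reasons, and any replacements of patients who withdrew before the intervention. SAP 5.5 reports "The number of eligible, consented patients who complete the Cytosponge™ procedure overall and in each subgroup". SAP 6.2.2 treats consent withdrawn before the procedure as non-consent, in a consent rate with a 95% CI.

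**The concern.** Protocol 1.3 puts swallowing first among the differences from Barrett's patients: "these patients already have dysphagia which could make swallowing of the capsule or retrieval of Cytosponge™ more difficult". A patient who agrees to the test and then cannot or will not try is informative about feasibility, yet leaves both numerator and denominator of the completion rate.

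The consent rate recovers only part of this group. Protocol 6 separates withdrawal from the study, which may be a clinical decision, from withdrawal of consent. A patient withdrawn under Protocol 13.1 for not receiving the device may never have withdrawn consent. That patient counts as a success in the consent rate, is absent from the completion rate, and is outside the acceptance rate, which covers only completers.

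At stake is what the go figure answers. As planned, it says how often those who try succeed. A surveillance programme also needs to know how often those who agree to the test complete it.

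**Working it through.** **Inputs.** 50 evaluable patients, assumed rate 70%, precision ±13 points (Protocol 13.1; SAP 3.3 specifies "asymptotic 95% CI, estimated 70% rate"). Go if the observed rate exceeds 70% (Protocol 14.5). Let *x* be completers among 50 attempters and *m* the consented patients who never attempt. The documents give no value for *m*; the range 0 to 10 is an assumption.

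**Plan's own figure.** Half-width = 1.96 × √(0.70 × 0.30 / 50) = 0.127, or ±12.7 points. The stated ±13 reproduces.

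**Smallest go result.** 35/50 is exactly 70% and does not exceed it, so 36/50 = 72.0% is the minimum.

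**Effect of the denominator.** The rate over all consented patients is *x*/(50 + *m*), with non-attempters counted as not completed. It is below *x*/50 whenever *m* > 0 and *x* > 0.

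| Completers among 50 attempters | m=0 | m=1 | m=2 | m=5 | m=8 | m=10 | Largest m still >70% |
|---|---|---|---|---|---|---|---|
| 36 | 72.0% | 70.6% | 69.2% | 65.5% | 62.1% | 60.0% | 1 |
| 38 | 76.0% | 74.5% | 73.1% | 69.1% | 65.5% | 63.3% | 4 |
| 40 | 80.0% | 78.4% | 76.9% | 72.7% | 69.0% | 66.7% | 7 |
| 45 | 90.0% | 88.2% | 86.5% | 81.8% | 77.6% | 75.0% | 14 |

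**Scale against sampling error.** The Wilson 95% interval is 58.3% to 82.5% for 36/50 and 55.7% to 80.1% for 36/52. The shift of 2.8 points (72.0 − 69.2) is small beside either interval. It matters because the go rule is a cut on the point estimate.

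**Sensitivity of the go probability.** Let *k* be the smallest count with *k*/(50 + *m*) > 0.70: 36 at *m* = 0, 37 at *m* = 2, 39 at *m* = 5 and 43 at *m* = 10. Then P(go) = P(X ≥ *k*), with X binomial(50, *p*) and *p* the true rate among attempters. The first results column is the planned rule. The others are hypothetical.

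| True rate among attempters | m=0 (planned) | m=2 | m=5 | m=10 |
|---|---|---|---|---|
| 70% | 0.447 | 0.328 | 0.139 | 0.007 |
| 75% | 0.748 | 0.637 | 0.382 | 0.045 |
| 80% | 0.939 | 0.889 | 0.711 | 0.190 |

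The design rate of 70% equals the threshold, so a result near the cut-off is one that the plan itself contemplates.

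**The case against.** The attempter-based rate is a declared quantity, defined the same way throughout both documents, and it is a reasonable primary measure of the procedure. This stands, and the fix keeps it.

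Several stronger readings are tempting, and the documents do not support them.

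- *Swallowing failures are dropped.* They are not. Attempted but failed swallows and assisted retrievals remain as failures; only patients who never attempt are lost.
- *Many patients will worsen between consent and procedure.* Entry requires a dysphagia score of 0 to 2 and the ability to swallow tablets. Consent and eligibility confirmation fall on day 1 or within the 7 days before. Protocol 6 expects early withdrawal to be rare. Any non-attempt rate is therefore an assumption.
- *Replacement inflates the rate.* Replacement fills the sample to 50 attempters. The denominator definition, not replacement, removes non-attempters from the figure.
- *Patients who refuse vanish.* Those who withdraw consent before the procedure count against the consent rate.
- *The decision rests on completion alone.* Protocol 14.5 also refers to the secondary objectives, though the >70% criterion itself uses only the completion rate.

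Counting every non-attempt as a failure also has its own bias. Protocol 8.3 steers neo-adjuvant patients towards the day of surgery, so a rescheduled operation could cause a non-attempt unrelated to the device.

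Much of the information can be derived from SAP 5.2 and 5.5. The content of SAP 5.1 on patient throughput is not visible in the text reviewed, so a flow chart may exist. What remains missing is a stated rate with an interval, and a link from it to the go decision.

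**Conclusion.** The point holds in a limited form. The planned completion rate is an upper bound on completion among consented patients, and a non-attempter who has not withdrawn consent is a failure in no planned rate. The direction is certain if any such patient exists; the size is not known from the documents.

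The go reading is fragile only near the threshold: two non-attempters reverse 36/50 and eight reverse 40/50, while 45/50 withstands 14. These counts assume 50 attempters and that every non-attempt is a failure. A reader might infer that the plan overstates feasibility by a material amount. The documents do not support that, because *m* may be zero or close to it. This is an inexpensive improvement to the analysis and does not invalidate the primary rate.

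**What to change.** 1. Keep the attempter-based completion rate as primary.
2. In SAP 6.2.1, add a supportive completion rate with 95% CI over all consented, registered patients, overall and for dCRT and naCRT separately, counting non-attempters as not completed.
3. Split non-attempts into patient- or device-related and logistic reasons (such as rescheduled surgery), and also show the rate with logistic non-attempts excluded.
4. State in Protocol 14.5 and SAP 3.7 that the go decision is read with both the primary and the supportive rate shown.
5. Reconcile the replacement trigger in Protocol 13.1 and SAP 3.3 (receipt of the intervention) with the evaluability definition in Protocol 14.1 (an attempt), so that a patient who tries and fails to swallow cannot be read as replaceable.

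**Cost.** A few rows in the primary table. Registration (Protocol 4.5), withdrawal reasons (Protocol 17.2, SAP 5.2) and type of chemoradiotherapy (SAP Table 2) are already recorded. The downside is a slightly lower second figure, partly driven by logistic non-attempts, which is why item 3 is needed. If there are no non-attempters, the two rates coincide and the result is shown to be robust.
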